To evaluate humoral immune responses of candidate SARS-CoV-2 variant vaccines, alone or in combination.

Secondary

1. To evaluate the safety of candidate SARS-CoV-2 variant vaccines, as assessed by:
 - Local and systemic solicited Adverse Events for 7 days following each vaccine dose.
 - Unsolicited Adverse Events from Dose 1 to 28 days following each vaccine dose.
 - SAEs, MAAEs, AESIs, NOCMCs, and AEs leading to withdrawal from the study from Dose 1 to 12 months after last vaccine dose.

Exploratory:

1. To assess, in at least a subset of samples, the B cell immune response of candidate SARS-CoV-2 variant vaccines.
2. To assess, in at least a subset of samples, the SARS-CoV-2 spike protein-specific T cell responses of candidate SARS-CoV-2 variant vaccines.
3. To assess, in at least a subset of samples, the magnitude, phenotype, and percentage of innate immune cells with candidate SARS-CoV-2 variant vaccines.
4. To assess, in at least a subset of samples, the functional potential of SARS-CoV-2 specific antibodies to mediate Fc-effector functions across candidate SARS-CoV-2 variant vaccines.
5. To evaluate breakthrough SARS-CoV-2 infection by sequencing strains for variant spike lineage and assessing anti- nucleocapsid serology.

Study Design:

This is a Phase 2 randomized open label, non-placebo controlled, multi-site, multi-stage clinical trial in individuals, 18 years of age and older, who are in stable state of health, have received a complete authorized/approved vaccine series (primary series + a booster either with homologous or heterologous vaccine products) \geq 16 weeks prior to enrollment.

Subjects will be stratified by i) age (18-64 years and \geq 65 years of age) (however arms 16 and 17 or stage 4 will only enroll participants between the ages of 18-49 years) and ii) history of confirmed prior SARS-CoV-2 infection, and randomly assigned to receive one of several variant vaccines. Enrollment will target a goal of approximately 45% of each of the variant vaccine arms to be in

older adults (≥ 65 years of age) for stages 1, 2 and 3 and approximately 20% to have had confirmed COVID-19 for all 4 stages.

This is an adaptive design and may add arms of new vaccine platforms and/or variant lineage spike vaccines as needed. The study arms will be conducted in different stages (that could overlap) depending on public health needs and availability of study products (starting with the available mRNA vaccines).

Table 1: Study Arms

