	Arms	Vaccine Platform	Sample Size	Vaccine Candidate	Interval (weeks)*	Timing of First Dose	Timing of Second Dose
Stage 1	1	Moderna mRNA-1273	100	Prototype	≥ 16	D1	NA
	2		100	Beta + Omicron	≥ 16	D1	NA
	3		100	Beta + Omicron	≥ 16	D1	D57
	4		100	Delta + Omicron	≥ 16	D1	NA
	5		100	Omicron	≥ 16	D1	NA
	6		100	Omicron + Prototype	≥ 16	D1	NA
Stage 2	7	Pfizer/ BioNTech BNT162b2	50	Wildtype (Prototype)	≥ 16	D1	NA
	8		50	Beta + Omicron	≥ 16	D1	NA
	9		50	Omicron	≥ 16	D1	NA
	10		50	Beta	≥ 16	D1	NA
	11		50	Beta + Wildtype	≥ 16	D1	NA
	12		50	Omicron + Wildtype	≥ 16	D1	NA
Stage 3	13	Sanofi CoV2 preS dTM-AS03	50	Prototype	≥ 16	D1	NA
	14		50	Beta	≥ 16	D1	NA
	15		50	Beta+ Prototype	≥ 16	D1	NA
Stage 4	16^	Pfizer/ BioNTech BNT162b2 bivalent	100	Omicron BA.1 + Wildtype (Prototype)	≥ 16	D1	NA
	17^		100	Omicron BA.4/BA.5 + Wildtype (Prototype)	≥ 16	D1	NA

Two age strata:

- 18-64 years
- ≥ 65 years (~45% in ≥ 65 years).

^For arms 16 and 17 or stage 4, only participants between the ages of 18 to 49 years will be enrolled.

Two infection strata:

- Confirmed prior SARS-CoV-2 infection (~20%)
- No known history of prior infection.

*interval (in weeks) since last exposure to SARS-CoV-2 infection or vaccination

Duration of Study: Up to 4 years

Duration of participation per subject: Up to 2 years (approximately 12 months after last inoculation)

Criteria for Inclusion/Exclusion:

Inclusion Criteria:

Participants must meet all of the following criteria to be eligible to participate in this study:

1. Individuals \geq 18 years of age at the time of consent (18-49 years for stage 4).
2. Confirmed receipt of a complete primary and booster COVID-19 vaccine series, either homologous or heterologous, with an FDA authorized/approved vaccine at least 16 weeks prior to study vaccine dose 1.
3. Willing and able to comply with all scheduled visits, vaccination plan, laboratory tests and other study procedures.
4. Determined by medical history, targeted physical examination and clinical judgement of the investigator to be in stable state of health.

Note: Participants with pre-existing stable chronic medical conditions defined as condition not requiring significant change in therapy or hospitalization for worsening disease within 4 weeks from enrollment, can be included at the discretion of the investigator.

Exclusion Criteria:

Participants meeting any of the following criteria will be excluded from the study:

1. Confirmed SARS-CoV-2 infection $<$ 16 weeks prior to any study vaccine dose.

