4. STUDY DESIGN

4.1 Overall Design

This is a Phase 2 randomized, adaptive, open label, non-placebo controlled multi-site, multi-stage clinical trial in individuals, 18 years of age and older, who are in stable state of health, have received a complete authorized/approved vaccine series (primary series + booster either with homologous or heterologous vaccine products) and meet all other eligibility criteria.

Approximately 1500 subjects will be enrolled at up to 30 clinical research sites. At enrollment, subjects will be stratified by i) age (18-64 and \geq 65 years of age) (however arms 16 and 17 or stage 4 will only enroll participants between the ages of 18-49 years) and ii) confirmed prior SARS-CoV-2 infection, and randomly assigned to one of several study arms of variant vaccines. The study will target the enrollment of approximately 45% of older adults (\geq 65 years of age) for stages 1, 2 and 3. Additionally, the study will target to enroll approximately 20% enrollment of participants with a history of confirmed SARS-CoV-2 infection. It is estimated that another 10-30% will have undiagnosed prior infection. Taken together, we anticipate about 40% of the total population will have prior infection. The study team will decide, based on latest epidemiology, if enrollment of participants in any particular groups are slowed in order to ensure good representation of previously infected and not previously infected.

The adaptive design of this study will include additional arms, an increase in sample size, or additional vaccine doses or different dosing and provide rapid information about the immunogenicity and the safety of candidate SARS-CoV-2 variant vaccines to inform near term public health policy. This trial will provide proof of concept on how variant vaccines could shift the immune response to become more specific to the VOCs' antigens or broaden the antigenic landscape for emergent variants.

Study arms and stages are described in [Section 1.1](#).

Screening can occur up to 28 days prior to the first dose of study product or on Day 1 prior to administration of Dose 1. Safety will be assessed during the study and blood will be drawn for immunogenicity assays at enrollment and in-person follow-up visits. Swabs will be self-collected or collected by staff at unscheduled illness visits to evaluate breakthrough SARS-CoV-2 infection (symptomatic infection or asymptomatic infection with a positive SARS-CoV-2 test outside the study).

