9.2 Sample Size Determination

9.2.1 Sample Size Calculation for the Safety Endpoint

Rare AEs are not demonstrable in a clinical study of this size; however, the probabilities of observing one or more AEs given various true event rates are presented in [Table 5](#). With the assumption that all enrolled subjects will likely complete immunizations and safety visits in this relatively short duration study, the following statistical considerations apply. With approximately 100 subjects in each arm there is a greater than 99.9% chance of observing at least one AE of probability 10%. With approximately 50 subjects in each of the strata subgroups (or arms), there is a 99.5% chance of observing at least one AE of probability 10%. With approximately 25 subjects in each of the strata subgroup combinations (assuming equal numbers and 100 per arm), there is a 92.8% chance of observing at least one AE of probability 10%. Finally, with approximately 15 subjects in the smallest of the strata subgroup combinations (assuming unequal numbers and 100 per arm or 50 per arm), there is a 79.4% chance of observing at least one AE of probability 10%. Therefore, if no AEs of a given type occur in a group (or strata), we can be relatively confident that they will occur in fewer than 10% of people if the vaccine is implemented.

Table 5: Probability of Observing one or more Adverse Event for Various Event Rates in one vaccine group (or strata).

N	“True” Event Rate	Probability of Observing \geq 1 events (%)	N	“True” Event Rate	Probability of Observing \geq 1 events (%)
100	0.1%	9.5	50	0.1%	4.9
	0.5%	39.4		0.5%	22.2
	1.0%	63.4		1.0%	39.5
	2.0%	86.7		2.0%	63.6
	3.0%	95.2		3.0%	78.2
	4.0%	98.3		4.0%	87
	5.0%	99.4		5.0%	92.3
	10.0%	>99.9		10.0%	99.5
	15.0%	>99.9		15.0%	>99.9
	20.0%	>99.9		20.0%	>99.9
	30.0%	>99.9		30.0%	>99.9

N	“True” Event Rate	Probability of Observing ≥ 1 events (%)	N	“True” Event Rate	Probability of Observing ≥ 1 events (%)
25	0.1%	2.5	15	0.1%	1.5
	0.5%	11.8		0.5%	7.2
	1.0%	22.2		1.0%	14
	2.0%	39.7		2.0%	26.1
	3.0%	53.3		3.0%	36.7
	4.0%	64.0		4.0%	45.8
	5.0%	72.3		5.0%	53.7
	10.0%	92.8		10.0%	79.4
	15.0%	98.3		15.0%	91.3
	20.0%	99.6		20.0%	96.5
	30.0%	>99.9		30.0%	99.5

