9.2.2 Sample Size Calculation for the Immunogenicity Endpoints

The primary objective of this study is to evaluate the magnitude and durability of SARS-CoV-2 specific antibody titers in serum samples. This objective is descriptive in nature and will be accomplished by estimating 95% confidence intervals (CI) for the geometric mean titer (GMT) at each timepoint when samples are collected.

The precision with which the GMT can be estimated from observed data depends on the standard deviation (SD) of the measurements, on the logarithmic scale, and the sample size. [Table 6](#) displays two-sided 95% confidence intervals for the GMT for several values of the observed antibody titer. [Table 6](#) also shows results assuming up to 10% attrition.

Table 6: Two-sided 95% confidence intervals based on observing a particular average \log_e -antibody titer in subjects' vaccine groups and potential strata sizes

Observed average \log_e antibody titer	SD of \log_e antibody titer	95% confidence interval of GMT in vaccine groups and strata			
		N = 100	N = 50	N = 25	N = 15
$\log_e(5)$	0.5	(4.5, 5.5)	(4.3, 5.8)	(4.1, 6.1)	(3.8, 6.6)
$\log_e(20)$		(18.1, 22.1)	(17.4, 23.1)	(16.3, 24.6)	(15.2, 26.4)
$\log_e(50)$		(45.3, 55.2)	(43.4, 57.6)	(40.7, 61.5)	(37.9, 66)
$\log_e(100)$		(90.6, 110.4)	(86.8, 115.3)	(81.4, 122.9)	(75.8, 131.9)
$\log_e(250)$		(226.4, 276.1)	(216.9, 288.2)	(203.4, 307.3)	(189.5, 329.8)
$\log_e(500)$		(452.8, 552.1)	(433.8, 576.3)	(406.8, 614.6)	(379.1, 659.5)
$\log_e(1000)$		(905.6, 1104.3)	(867.5, 1152.7)	(813.5, 1229.2)	(758.1, 1319)
$\log_e(5)$	1.0	(4.1, 6.1)	(3.8, 6.6)	(3.3, 7.6)	(2.9, 8.7)

Observed average \log_e antibody titer	SD of \log_e antibody titer	95% confidence interval of GMT in vaccine groups and strata			
		N = 100	N = 50	N = 25	N = 15
\log_e (20)		(16.4, 24.4)	(15.1, 26.6)	(13.2, 30.2)	(11.5, 34.8)
\log_e (50)		(41, 61)	(37.6, 66.4)	(33.1, 75.6)	(28.7, 87)
\log_e (100)		(82, 121.9)	(75.3, 132.9)	(66.2, 151.1)	(57.5, 174)
\log_e (250)		(205, 304.9)	(188.2, 332.2)	(165.5, 377.8)	(143.7, 435)
\log_e (500)		(410, 609.7)	(376.3, 664.3)	(330.9, 755.5)	(287.4, 869.9)
\log_e (1000)		(820, 1219.5)	(752.6, 1328.7)	(661.8, 1511)	(574.8, 1739.8)

* Assumes approximately 10% attrition.

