9.4.7 Sub-Group Analyses

Subgroup analyses, by age group and infection status, may be performed. Detailed information will be provided in the Statistical Analysis Plan.

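### Section 9.2.1 puts about 15 subjects in the smallest age-by-infection cell; the protocol's own targets give about 9 in Stage 1 arms and 4 to 5 in Stage 2 and 3 arms, and 15 is impossible in a 50-subject arm

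*Protocol*

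**What the plan says.** Section 9.2.1 works down from whole arms to subgroups. It takes 25 subjects per strata combination when an arm of 100 is split equally, so it has four cells per arm in mind. For unequal splits it continues "with approximately 15 subjects in the smallest of the strata subgroup combinations (assuming unequal numbers and 100 per arm or 50 per arm" and attaches a probability of 79.4% for an AE with a true rate of 10%. The paragraph closes by saying that if no AE of a given type is seen in a group or stratum, "we can be relatively confident that they will occur in fewer than 10% of people if the vaccine is implemented".

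Table 5 (section 9.2.1) has an N = 15 block. Table 6 (section 9.2.2) has an N = 15 column under the heading "95% confidence interval of GMT in vaccine groups and strata".

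The cell sizes follow from the synopsis (section 1.1) and section 4.1. There are two age strata (18 to 64, and 65 or over) and two infection strata (confirmed prior infection, or no known history). About 45% of each arm is to be 65 or over "for stages 1, 2 and 3 and approximately 20% to have had confirmed COVID-19 for all 4 stages". Table 1 gives 100 subjects per arm in Stages 1 and 4, and 50 per arm in Stages 2 and 3 (nine arms, 7 to 15). Its footnote says "For arms 16 and 17 or stage 4, only participants between the ages of 18 to 49 years will be enrolled". Section 4.1 adds: "It is estimated that another 10-30% will have undiagnosed prior infection", for about 40% with any prior infection.

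Section 9.4.7 says "Subgroup analyses, by age group and infection status, may be performed".

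**The concern.** The sentence gives one smallest-cell size for two arm sizes that differ by a factor of two. For the smaller arms that size is larger than an equal four-way split would allow. For the larger arms it does not match the enrollment targets.

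Section 9.2 is where a reader learns what the age and infection subgroups can support, and these are the trial's only stratification factors. If the cells are a half to a third of the stated size, both the chance of seeing an AE and the precision of the geometric mean titer (GMT) are overstated. The closing sentence is worded to cover strata. A cell with no events could therefore be read as evidence against a 10% event rate when seeing none is quite likely at that rate.

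**Working it through.** **1. Reproduce the plan's figures.** The chance of at least one event is 1 − (1 − p)^n. At p = 0.10 this gives 92.8% for n = 25 and 1 − 0.9^15 = 79.4% for n = 15, as printed. The other numeric entries of Table 5 also reproduce.

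Table 6 follows GMT × exp(± t(0.975, n − 1) × SD/√n). At n = 15, SD 1.0 and GMT 100 this gives (57.5, 174.0), as printed. The tables are computed correctly; only the cell size is in question.

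**2. Upper limit without using the targets.** The smallest of four cells cannot exceed a quarter of the arm. For 50 subjects that is 50/4 = 12.5, so at most 12. A smallest cell of 15 cannot occur.

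**3. Cell sizes under the targets.** Inputs: 45% aged 65 or over, 20% confirmed infected. The smallest cell is those 65 or over with confirmed infection.

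- Stage 1: 100 × 0.45 × 0.20 = 9
- Stages 2 and 3: 50 × 0.45 × 0.20 = 4.5

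These products assume that age and infection are independent. Without that assumption, the infection target alone caps the smaller infected cell at 20/2 = 10 (100 per arm) or 10/2 = 5 (50 per arm).

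- Stage 4 has one age group, so its smallest stratum is the infected one: 100 × 0.20 = 20

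**4. What a cell of 15 would need.** In a 100-subject arm, 15/45 = 33.3% infected. In a 50-subject arm, 15/22.5 = 66.7% infected; the uninfected cell aged 65 or over would then be 22.5 − 15 = 7.5, and 15 would no longer be the smallest.

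**5. Counting undiagnosed infection.** This raises the infected share to 30% to 50%.

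| Infected share | Cell per 100 | Cell per 50 |
|---|---|---|
| 30% | 13.5 | 6.75 |
| 40% | 18 | 9 |
| 50% | 22.5 | 11.25 |

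**6. Consequences for safety at a true rate of 10%.** The zero-event bound is the one-sided 95% upper limit, 1 − 0.05^(1/n). It is given for illustration, since the protocol names no confidence level.

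| n | Where it applies | At least one event | No event | Zero-event bound |
|---|---|---|---|---|
| 15 | stated | 79.4% | 20.6% | 18.1% |
| 12 | best possible, 50-subject arm | 71.8% | 28.2% | 22.1% |
| 9 | Stage 1 | 61.3% | 38.7% | 28.3% |
| 5 | Stages 2 and 3 | 41.0% | 59.0% | 45.1% |
| 4 | Stages 2 and 3 | 34.4% | 65.6% | 52.7% |
| 20 | Stage 4, infected | 87.8% | 12.2% | 13.9% |

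**7. Consequences for the GMT interval (GMT 100).**

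| n | SD 0.5 | SD 1.0 |
|---|---|---|
| 15 (stated) | (75.8, 131.9) | (57.5, 174.0) |
| 9 | (68.1, 146.9) | (46.4, 215.7) |
| 5 | (53.7, 186.0) | (28.9, 346.1) |

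**The case against.** The strongest reply is that infection status in the subgroup analysis may mean any prior infection. Section 4.1 expects about 40% on that basis and lets the team slow enrollment to balance the groups. A Stage 1 cell would then be about 18, and 15 would be cautious. This stands for Stage 1 if that is the intended definition. However, the stratum defined in the synopsis and section 4.1 is confirmed infection, and even at 40% a 50-subject arm reaches only 9.

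The figures 9 and 4.5 also assume independence of age and infection, which the protocol does not state. That is true, but the caps of 10 and 5 need no such assumption and still exclude 15.

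Tables 5 and 6 can be read as general lookup tables, correct at N = 15. Also true; but section 9.2.1 expressly assigns 15 to the smallest combination, and the tables offer nothing smaller.

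The closing inference about rates below 10% is weak even at larger cells: by the bound used above, zero events leave 18.1% at n = 15 and 1 − 0.05^(1/25) = 11.3% at n = 25. The cell-size error makes that weakness worse but does not create it.

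Table 6 carries a note about 10% attrition, so one might reduce 9 and 5 further. The printed intervals use the full N, so N = 9 and N = 5 follow the table's own convention.

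Finally, the trial tests no hypothesis, subgroup analyses are optional, and the halting rules in section 7.1.1 count events by arm. This limits the weight of the point but does not make the sentence correct.

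**Conclusion.** The statement is wrong as written. For the nine 50-subject arms it is impossible under any split. For Stage 1 it contradicts the confirmed-infection target, and it could be defended only if undiagnosed infection were counted.

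Under the stated targets, with age and infection taken as independent, the 79.4% should be 61.3% in Stage 1 and 34.4% to 41.0% in Stages 2 and 3. At n = 4 or 5, seeing no event is more likely than not when the true rate is 10%.

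The N = 100 and N = 50 whole-arm figures stand, and enrollment numbers and halting rules do not depend on the 15. The point should be corrected because it misstates what the stratified cells can show.

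**What to change.** In section 9.2.1, replace the sentence on the smallest combination with wording such as:

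> Under the enrollment targets, and assuming that age and infection status are independent, the smallest age-by-infection cell has about 9 subjects in Stage 1 arms and 4 to 5 in Stage 2 and 3 arms. The chance of seeing one or more AEs with a true rate of 10% is then 61.3%, and 34.4% to 41.0%, respectively. Stage 4 has one age group; its smallest stratum, prior infection, has about 20 subjects (87.8%).

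This removes the reference to 15 subjects in 50-subject arms. In Tables 5 and 6, replace N = 15 with N = 9 (Stage 1) and N = 5 (Stages 2 and 3).

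State that the closing inference about rates below 10% does not extend to these smallest cells. Since n = 25 also misses 10% by the bound above, confining it to groups of 50 or more would be cleaner (1 − 0.05^(1/50) = 5.8%).

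If infection status is meant to include undiagnosed infection, say so. N = 15 could then stay for Stage 1 only.

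The cost is one sentence, one qualification and recomputed columns in two tables. No subjects or procedures are added; the only downside is that the stated figures become less favorable.

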9.4.4 Safety Analyses

Summaries and analysis of safety data will be presented for the Safety Analysis Population.

Solicited non serious AEs will be collected from the time of each vaccination until 7 days after. Solicited AEs will be summarized by severity for each day post vaccination (Days 1-8) and as the maximum severity over all 8 days. Additionally, solicited AEs will be analyzed using standard techniques, such as exact confidence intervals (CI), to summarize the proportion of subjects reporting each symptom, any application site symptom, and any systemic symptom.

Unsolicited non-serious AEs will be collected from the time of first vaccination through 28 days after each vaccination. Unsolicited AEs will be coded by MedDRA for preferred term and system organ class (SOC). SAEs, MAAEs, NOCMCs, AESIs, and AEs leading to withdrawal from the study will be collected from the time of first vaccination through 12 months after the last vaccine dose. The numbers of SAEs, MAAEs, NOCMCS, AESIs, and AEs leading to withdrawal from the study will be reported by detailed listings showing the event description, MedDRA preferred term and SOC, relevant dates (vaccinations and AEs), severity, relatedness, and outcome for each event. Non-serious unsolicited AEs will be summarized as number and percentage of subjects reporting at least one event in each MedDRA preferred term and SOC, cross tabulated by severity and relationship to study product. Additionally, the proportion of subjects and exact 95% CIs of AEs in aggregate and by MedDRA categories will be computed.

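### Section 9.2.1 draws one zero-event conclusion (true rate below 10%) for every group and stratum size it lists, but the figures do not support it at N=15 and only marginally at N=25

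*Protocol*

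**What the plan says.** Protocol section 9.2.1 takes four group sizes and gives, for each, the chance of seeing at least one AE when the true rate is 10%. For about 100 per arm it is above 99.9%. For about 50 (a stratum subgroup or a smaller arm) it is 99.5%. For about 25 (a combination of strata, equal numbers assumed), "there is a 92.8% chance of observing at least one AE of probability 10" percent. For about 15 (the smallest combination of strata), "there is a 79.4% chance of observing at least one AE of probability 10" percent. Table 5 repeats these values among others, under a title that covers a vaccine group or stratum.

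The paragraph closes with a consequence introduced by the word therefore: where "no AEs of a given type occur in a group (or strata), we can be relatively confident that they will occur in fewer than 10" percent of people once the vaccine is in use. No confidence level is attached, and the sentence is not restricted to any of the four sizes.

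For the analysis itself, section 9.4.4 plans that "the proportion of subjects and exact 95% CIs of AEs in aggregate and by MedDRA categories will be computed".

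**The concern.** The closing sentence treats four very different amounts of information alike. With zero events, what can be said about the true rate depends almost entirely on the number of subjects. A group of 100 bounds the rate tightly; a stratum of 15 does not. Because the sentence refers to strata as well as groups, and follows directly from a list that includes 25 and 15, it extends the reassurance to sizes that may not carry it.

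At stake is how the absence of an AE in a small stratum should be understood. A reader who took the sentence at face value for a 15-subject stratum would regard a 10% rate as reasonably ruled out, when a true 10% AE would often leave no trace there.

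**Working it through.** **Inputs.** The sizes 100, 50, 25 and 15 and the true rate of 10% are from section 9.2.1. That section names no confidence level; 95% with an exact interval is taken from section 9.4.4. As in 9.2.1, no dropout is assumed.

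**Step 1: reproduce the plan's figures.** The chance of at least one event is 1 − (1 − p)^N. With p = 0.10:

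- N=100: 1 − 0.9^100 = 99.997% (plan: above 99.9%)
- N=50: 1 − 0.9^50 = 99.5% (plan: 99.5%)
- N=25: 1 − 0.9^25 = 92.8% (plan: 92.8%)
- N=15: 1 − 0.9^15 = 79.4% (plan: 79.4%)

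All 44 cells of Table 5 reproduce to rounding with the same formula.

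**Step 2: chance of missing a 10% AE altogether.** This is 0.9^N: 0.5% at N=50, 7.2% at N=25 (about 1 in 14) and 20.6% at N=15 (about 1 in 5).

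**Step 3: upper limit for the true rate after zero events.** The one-sided 95% limit is 1 − 0.05^(1/N). The upper end of the two-sided exact (Clopper-Pearson) 95% interval is 1 − 0.025^(1/N).

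| N | Missed at true rate 10% | Upper limit, one-sided 95% | Upper limit, two-sided exact 95% |
|---|---|---|---|
| 100 | under 0.1% | 3.0% | 3.6% |
| 50 | 0.5% | 5.8% | 7.1% |
| 25 | 7.2% | 11.3% | 13.7% |
| 15 | 20.6% | 18.1% | 21.8% |

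**Step 4: size needed for zero events to exclude 10%.** Solve 0.9^N ≤ 0.05: N ≥ ln 0.05 / ln 0.9 = 28.4, so 29 subjects (one-sided 95%). Solve 0.9^N ≤ 0.025: N ≥ 35.01, so 36 subjects (two-sided 95%). Both thresholds lie between the 25 and the 50 listed in 9.2.1.

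**Step 5: read the plan's own figures as confidence levels.** With zero events, the one-sided confidence that the rate is below 10% is 1 − 0.9^N, which is the detection chance already printed. The one phrase therefore stands for more than 99.9% confidence at N=100 and for 79.4% at N=15.

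**The case against.** The sentence is hedged. It speaks of being relatively confident, names no 95% level, and does not say that zero events establishes a rate below 10%. Judged by its own words, 92.8% at N=25 can fairly be called relative confidence. The qualifying figures are also in plain view: 92.8% and 79.4% appear immediately before the conclusion and again in Table 5, and the section opens by conceding that rare AEs cannot be demonstrated in a study of this size. This stands. It makes N=25 a borderline case and leaves N=15 as the real weakness. It does not rescue N=15, where the support is 79.4% and the wording is the same as for a whole arm of 100.

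Three stronger readings are tempting, and the documents do not support them.

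- A reader might infer that a number in the safety calculation is wrong. None is; only the summary drawn from the numbers is too broad.
- A reader might infer that 9.2.1 contradicts the safety analysis. Section 9.4.4 states a method, not a conflicting figure, and exact intervals produced for a small stratum would themselves display the wide upper limits.
- A reader might infer that the sentence will govern how empty AE rows in age-by-infection cells are interpreted. Nothing says so. Section 9.4.7 only allows that subgroup analyses by age group and infection status may be performed, with detail left to the SAP.

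The choice between one-sided and two-sided limits is a convention that 9.2.1 does not settle. N=15 and N=25 exceed 10% under either, and N=50 and N=100 stay below it under either.

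**Conclusion.** The conclusion in section 9.2.1 is wrong as written for the smallest stratum and too loose for the next smallest. It is sound at N=100 and N=50. At N=25 the upper limit passes 10% by 1.3 percentage points one-sided (11.3%) or 3.7 two-sided (13.7%). At N=15 it is about twice the stated bound (18.1% or 21.8%).

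These limits rest on a 95% level borrowed from 9.4.4, on complete follow-up as 9.2.1 assumes, and on strata of the sizes named there. The miss probabilities of 7.2% and 20.6% need no choice of confidence level, being the complements of the protocol's own figures.

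Severity is low. Section 9.1 states that the trial tests no specific hypothesis, the halting criteria in section 7.1.1 are triggered by observed events, and no sample size follows from the sentence.

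**What to change.** Change the last sentence of the first paragraph of section 9.2.1 in one of two ways:

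- Restrict the statement about rates below 10% to the N=50 and N=100 groups.
- Preferably, replace it with size-specific limits: when no AEs of a given type are seen, the upper limit of the exact two-sided 95% confidence interval is 3.6% for 100 subjects, 7.1% for 50, 13.7% for 25 and 21.8% for 15. Naming the interval type matches the exact 95% intervals planned in section 9.4.4 and settles the question of sidedness.

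Table 5 and the detection chances in the text stay as they are. The cost is one sentence of text and a less favourable statement for the small strata. Enrolment, procedures and planned analyses are unaffected.
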